1.2 BACKGROUND AND RATIONALE

Radiation is an effective therapy for localized prostate cancer. Although most patients are cured of their prostate cancer by external beam radiation therapy (EBRT) and/or brachytherapy, a subset of patients will develop biochemical failure, defined as a rise in the PSA of more than 2 ng/dL above the post radiation nadir. The risk of biochemical recurrence after irradiation using more modern approaches varies greatly depending on pretreatment risk grouping. Biochemical recurrence rates may be as high as 50% for patients categorized as high risk (1). The natural history of local recurrence is largely unknown, as most patients that develop a biochemical recurrence after radiotherapy have been treated with androgen suppression without further investigation of the site of failure. Indeed, although biochemical failure rates are well known after irradiation, patterns of failure are only now being determined with the development of improved staging modalities, such as multiparametric MRI.

Patients with biochemical failure may harbor local recurrence or metastatic disease. Immediate or delayed androgen deprivation therapy, a non-curative therapy, is most often used for treatment of these patients (2). Data from prospective studies including prostate biopsies after EBRT have suggested that local persistence of disease serves as a source of metastases and contributes to a reduction in disease free survival (3).

In the absence of metastatic disease, local salvage therapies offer a potentially curative treatment option for patients with a local recurrence after prostate radiotherapy; however, many of these therapeutic approaches are associated with substantial treatment morbidity and remain underutilized (4). The most commonly used options for salvage after radiation include cryoablation (5-10), prostatectomy (11-13), and re-irradiation (14-22). Developing less toxic local salvage therapies may provide a more acceptable curative treatment option for these patients.

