6.3.2 Response Criteria

Biochemical control: Biochemical control will be defined using the Phoenix criteria (47). The post-SBRT nadir is the lowest PSA measurement obtained after treatment on this protocol. Biochemical control is defined as a serum PSA less than or equal to 2 ng/dL above the post-SBRT nadir.

Biochemical progression/biochemical failure: Serum PSA more than 2 ng/dL above the post-SBRT nadir. At least 2 PSA measurements separated by 1 month are needed to confirm biochemical failure.

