6.3.3 Progression-Free Survival

Biochemical progression free survival (bPFS) will be evaluated on this trial as a secondary endpoint. bPFS is defined as the duration of time from start of treatment to time of PSA progression or death, whichever occurs first. PSA progression (also known as biochemical failure) is defined based on elevation of PSA 2 ng/dL beyond the post-treatment nadir PSA, using the Phoenix criteria (47). A total of 2 PSA values separated by at least 1 month are required to document biochemical recurrence and to reduce the risk of mistakenly classifying a PSA “bounce” as a failure. If the PSA remains elevated, the date of failure will be backdated to the first PSA measurement that exceeded 2 ng/dL above the nadir. Only PSA values collected at the NIH Clinical Center will be used to evaluate disease status given the variability in ranges obtained in different laboratories. Patients who have been treated with androgen deprivation therapy within 3 months before or during this study will not be evaluable for the bPFS endpoint

until their testosterone is within the institutional limit of normal for at least two sequential measurements spaced by 1 month.

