11.4.2 Benefits

The potential benefits of trial participation relate to potential curative treatment of recurrent prostate cancer. Many patients do not have a curative option after local failure following radiation treatment. This protocol would provide a potentially curative option. Currently, therapy for biochemical failure typically consists of the temporizing use of hormonal therapy if a patient is not a suitable candidate for other ablative treatments.

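### Section 6.3.3 suspends bPFS evaluability for androgen deprivation even when it is started for suspected relapse, so 2-year bPFS can be overstated

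*Combined protocol and SAP*

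**What the plan says.** Section 6.3.3 defines the endpoint: "bPFS is defined as the duration of time from start of treatment to time of PSA progression or death, whichever occurs first". PSA progression is a rise of 2 ng/dL over the post-treatment nadir, and "A total of 2 PSA values separated by at least 1 month are required to document biochemical recurrence". Section 6.3.2 has the same requirement: "At least 2 PSA measurements separated by 1 month are needed to confirm biochemical failure". Once the rise is confirmed, "the date of failure will be backdated to the first PSA measurement that exceeded 2 ng/dL above the nadir". Starting salvage treatment is not an event.

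The same section then sets the ADT rule: "Patients who have been treated with androgen deprivation therapy within 3 months before or during this study will not be evaluable for the bPFS endpoint". The sentence does not stop there. A second half limits how long this state lasts, namely "until their testosterone is within the institutional limit of normal for at least two sequential measurements spaced by 1 month". The rule is therefore a suspension that ends with testosterone recovery. It takes no account of why ADT was given, or whether it came before, with or after SBRT.

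Other sections bear on this:

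- Section 10.3 makes a man evaluable for biochemical outcomes once he has one PSA after treatment, with no ADT condition.
- Section 10.4.3 names Kaplan-Meier for bPFS but gives no censoring rule.
- The calendar in section 3.6 marks testosterone at screening/baseline only.
- Section 4 permits concurrent ADT but discourages it.
- Section 6.1.1 lists ADT use among the captured data, but not the reason for it.
- Section 10.1 expects bPFS to compare well with a 75% brachytherapy rate.

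**The concern.** Suspending evaluability makes sense for ADT given before or with SBRT, because the PSA is then suppressed for a reason unrelated to how SBRT worked. ADT started later because relapse is suspected is different: it is a consequence of the outcome being measured.

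The path is short. A first PSA exceeds nadir + 2, ADT begins, the PSA falls, the second value does not confirm, and no event exists. The man is also suspended, and his return depends on two testosterone values that the calendar does not schedule, within a follow-up that ends at 24 months.

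The protocol makes ADT after relapse foreseeable. Section 1.2 says "Immediate or delayed androgen deprivation therapy, a non-curative therapy, is most often used for treatment of these patients", and section 11.4.2 says "therapy for biochemical failure typically consists of the temporizing use of hormonal therapy". Note 11 to the calendar also lets PSA be drawn locally, while section 6.3.3 counts only values from the Clinical Center. That can lengthen the gap between a visible rise and a countable confirmation.

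Kaplan-Meier assumes that censored men have the same outlook as those still followed. These men do not, so dropping or censoring them pushes bPFS up, in the direction of the favourable comparison in section 10.1. Using section 10.3 instead does not cure this: the man stays in the set with a suppressed PSA and still has no event.

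**Working it through.** The plan gives no precision or sample-size figure for bPFS, so there is none to reproduce. The check asks how far the estimate moves when a share f of the men who relapse by 24 months start ADT before confirmation.

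**Inputs**

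- True 2-year bPFS S = 75% (comparison rate, section 10.1), or 82% (earlier SBRT series, section 1.2.1).
- n = 42, the maximum number of evaluable men in section 10.2.
- f = 20% or 30%: assumed.
- Time to re-entry R = 6 or 12 months: assumed.
- Constant hazard: assumed.

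**Formulas**

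1. Men removed for good: S / [S + (1 − S)(1 − f)].
2. Men censored at ADT start and never returning: S^(1 − f).
3. Men re-entering after R months, with failure dated then: 1 − [(1 − f)F(24) + f·F(24 − R)], where F(t) = 1 − S^(t/24).

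**Results for S = 75%**

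F(24) = 0.250, F(18) = 1 − 0.75^0.75 = 0.194 and F(12) = 1 − 0.75^0.5 = 0.134.

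| Handling | f = 20% | f = 30% |
|---|---|---|
| Removed | 0.75/0.95 = 78.9% | 0.75/0.925 = 81.1% |
| Censored | 0.75^0.8 = 79.4% | 0.75^0.7 = 81.8% |
| Re-entry at 6 months | 1 − (0.200 + 0.0388) = 76.1% | 1 − (0.175 + 0.0582) = 76.7% |
| Re-entry at 12 months | 1 − (0.200 + 0.0268) = 77.3% | 1 − (0.175 + 0.0402) = 78.5% |

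The binomial standard error is √(0.75 × 0.25/42) = 6.7 points; simulation gave 6.6. With 6.6, permanent loss shifts the estimate by 0.6-0.7 SE at f = 20% and by 0.9-1.0 SE at f = 30%. With re-entry the shifts are 0.17-0.35 SE and 0.25-0.53 SE.

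**Results for S = 82%**

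Permanent loss gives 0.82/0.964 = 85.1% (removed) or 0.82^0.8 = 85.3% (censored) at f = 20%. At f = 30% it gives 0.82/0.946 = 86.7% or 0.82^0.7 = 87.0%.

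**Simulation check**

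The check used 3,000 trials of 42 men, visits at 1, 3, 6 and then every 3 months to 24, and true bPFS 75%. At f = 25% it gave 80.1% (removed), 80.8% (censored), 76.3% (6-month re-entry) and 77.8% (12-month re-entry). Counting ADT for relapse as an event gave 75.0%.

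**Small-number illustration**

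In one arm of 21 with 5 failures, bPFS is 16/21 = 76.2%. If 2 of the 5 are removed it becomes 16/19 = 84.2%.

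**The case against.** The strongest reply is that the rule is narrower than it looks, and much of that stands.

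- A reader might infer that any man given ADT is removed permanently. The text does not say so: the sentence ends with testosterone recovery. If re-entry works and he is then counted, the bias is about half the permanent-loss figure or less. The reply is weakened because the calendar does not schedule the testosterone values needed.
- A reader might infer that a failure already confirmed is erased when ADT follows. That is strained. bPFS is time to first event and a confirmed failure is backdated, so such a man naturally keeps his event and adds no bias. The text does not state it, so it is worth stating.
- A reader might infer that every man lost this way is a true failure. Section 6.3.3 requires two values because one rise may be a bounce, so some of these men may not have failed.
- Sections 1.2 and 11.4.2 describe ADT used for biochemical failure. They do not show how often it precedes confirmation. Note 11 calls for a confirming PSA, and section 4 discourages concurrent ADT. The documents therefore support saying that bPFS can be overstated, not that it is.
- One might also want imaging- or biopsy-proven relapse without salvage treatment counted as events. Repeat PET is done once and only in some men, and no follow-up biopsy is scheduled, so ascertainment would be uneven. That addition is not recommended.

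bPFS is also a secondary, descriptive endpoint in a phase I trial, and no test against 75% is planned. This limits the stakes but does not supply the missing rule.

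**Conclusion.** The concern holds in a limited form. Section 6.3.3 has no exception for ADT started after SBRT because of suspected relapse, and no section counts that ADT as a failure. When it precedes the confirming PSA, the man is lost to the estimate for a reason tied to the outcome, and the error runs mainly upward.

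At a true rate of 75%, the overstatement is about 4 points (f = 20%) to 6-7 points (f = 30%) if the men never return, and about 1 to 3.5 points over the same range of f if they re-enter after 6-12 months. The figures rest on assumed values of f and re-entry time and on a constant hazard. They also treat every man on this path as a true failure, so bounces would reduce the bias. The SE multiples use the maximum of 42 men; with fewer, the SE grows while the bias in points does not.

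Sections 6.3.3 and 10.3 also give different evaluable sets, which leaves a choice open after the data are seen. The point deserves correction before analysis but does not touch the primary endpoint.

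**What to change.** Change the counting rules as follows:

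1. In section 6.3.3, limit the suspension to ADT not started for relapse.
2. State that a failure confirmed before ADT stands.
3. Count ADT or other salvage treatment started after SBRT for suspected or proven relapse as a bPFS event, dated at the earlier of the first PSA above nadir + 2 or the salvage start.
4. Add a sensitivity analysis that censors at salvage start, because a single unconfirmed rise may be a bounce. The two results show how far the conclusion depends on these men.
5. Record the reason for ADT alongside its use.
6. Reconcile section 6.3.3 with the evaluability rule in section 10.3, and put the event and censoring rules in section 10.4.3.

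The cost is protocol wording and one data item: ADT use is already captured and concomitant medications are monitored throughout. The small downside is that bPFS may be slightly lower and is no longer strictly a PSA-only count, which slightly loosens comparison with the earlier SBRT series reported by Phoenix criteria. The change affects only how outcomes are counted, not whether any man receives ADT.

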2.2 SCREENING EVALUATION

Note: Screening evaluation testing/procedures are conducted under the separate screening protocol, 01-C-0129 (Eligibility Screening and Tissue Procurement for the NIH Intramural Research Program Clinical Protocols). Assessments performed at outside facilities or on another NIH protocol within the timeframes below may also be used to determine eligibility once a participant has signed the consent.

- Clinical Evaluation: Complete history and physical examination, including weight and performance status within 4 weeks of study entry.
- Laboratory Evaluation: CBC with differential, chemistries (to include creatinine BUN, PSA, testosterone, Alk Phos, ALT, AST, Bilirubin), PT, PTT within 4 weeks of study entry.
- Viral serologies: HIV screening within 4 weeks of study entry
- Radiographic Evaluation: Whole body bone scan, F18 NaF PET, and multiparametric MRI of the prostate. In selected patients, a CT of the abdomen and pelvis (with oral and IV contrast) may also be obtained for staging, particularly if MRI is not felt to adequately have staged the pelvic and abdominal lymph nodes. All imaging studies should be completed within 3 months of study entry. MRI of the prostate obtained more than 3 months (no greater than 5 months prior to entry) may be used if a biopsy has recently been performed, as post-biopsy MRI may not be easily interpretable due to hemorrhage.

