2.4 BASELINE EVALUATION

- Clinical evaluation: clinical assessment with attention to any new medications or interventions since screening history and physical examination (to be completed within 2 weeks of study entry, screening history and physical examination is acceptable if obtained within the 2-week interval)
- Laboratory evaluation: CBC with differential, BUN, Creatinine, Alk Phos, ALT, AST, Total Bilirubin, PSA, Testosterone, PT, PTT, Hepatitis B, and Hepatitis C (within 4 weeks of study entry)
- 18F-DCFPyL imaging (will not be repeated if performed on a different protocol within 4 months prior to study enrollment).
- Post-Imaging research and diagnostic biopsies of areas in the prostate identified as suspicious and systematic biopsy. If recent systematic biopsies were obtained (within 5 months) systematic biopsies will not be repeated. Fiducial markers to guide radiation

treatment will be implanted simultaneously if not previously placed or visible

- Questionnaires (to be completed prior to treatment and within 2 weeks prior to SBRT). See Section [3.4](#) for further details. Expanded Prostate Cancer Index Composite (EPIC-26), SHIM, AUA-SI, PROMIS Depression SF4a, PROMIS Anxiety SF4a, PROMIS Psychological Impact Positive SF 4a, Decision Regret Scale
- Correlative assays (to be completed prior to treatment and within 2 weeks prior to SBRT). See Section [5.1](#) for further details. Collection of Plasma – three 8 cc EDTA), urine (15cc in a sterile cup), and research biopsies. In patients with active Hepatitis B or C, some research blood work may not be drawn.

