3.6 STUDY CALENDAR

| Procedure | Screening/ Baseline | Active SBRT treatment | Post Therapy Follow-up (1, 3 mos) 15 | Post Therapy Follow-up 6 months post-SBRT | Post Therapy Follow-up (9 mos and q 3 mos until 24 mos) 8 | |
|--|------------------------|-----------------------------|---|--|---|--|
| History and PE | X | | | | | |
| Vital signs 10 | X | | X | X | X | |
| Performance Score | X | | | | | |
| Weight | X | | | | | |
| Labs | | | | | | |
| CBC, Acute care panel, LFTs, Testosterone, PT/PTT, Viral serologies 2 | X | | | | | |
| PSA 4 | X | | X 11 | X 11 | X 11 | |
| Biopsies (ultrasound guided)/fiducials 5 | X | | | | | |
| mpMRI 3 | X 3 | | | X 12 | | |
| 18F-DCFPyL PET/CT imaging | X 7 | | | X 6, 12 | | |
| 18F-NaF PET/CT imaging 3 | X | | | | | |
| Whole body bone scan 3 | X | | | | | |
| Clinical evaluation | | X | X 9 | X 9 | X 9 | |
| Adverse Events | X | | Monitored continuously | | | |
| Concomitant Medications | X | | Monitored continuously | | | |
| Correlatives | | | | | | |
| Research Biopsy 5 | X | | | | | |
| Blood 12 | X | X 1 | X | X | X | |
| Urine 12 | X | | X | X | X | |
| Questionnaires | | | | | | |
| EPIC-26, SHIM, AUA-SI, DRS, PROMIS 13, 14 | X | | X | X | X | |

1. Correlative blood sampling should be performed within 24 hours after the last dose of irradiation.
2. CBC with differential, chemistries (to include creatinine BUN, PSA, testosterone, Alk Phos, ALT, AST, Bilirubin), PT, PTT within 4 weeks of study entry. Viral serologies: HIV, Hepatitis B, and Hepatitis C screening within 4 weeks of study entry. Acute Care Panel: (Sodium (NA), Potassium (K), Chloride (CL) Total CO₂ (Bicarbonate), Creatinine, Glucose, Urea nitrogen, eGFR).
3. Whole body bone scan, F18 NaF PET, and multiparametric MRI of the prostate. In selected patients, a CT of the abdomen and pelvis (with oral and IV contrast) may also be obtained for staging, particularly if MRI is not felt to adequately have staged the pelvic and abdominal lymph nodes. All imaging studies should be completed within 3 months prior to study entry. MRI of the prostate obtained more than 3 months (no greater than 5 months prior to entry) may be used if a biopsy has recently been performed, as post-biopsy MRI may not be easily interpretable due to hemorrhage.

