4. PSA failure after definitive radiation as defined by the Phoenix criteria (PSA elevation at least 2 ng/dL above post-radiotherapy nadir). Serial PSA and serial correlative studies will be collected for two years post-treatment.
5. Post-Imaging research and diagnostic biopsies of areas in the prostate identified as suspicious and systematic biopsy. If recent systematic biopsies were obtained (within 5 months) systematic biopsies may not be repeated. Fiducial markers to guide radiation treatment will be implanted simultaneously. If biopsy tissue was obtained within 5 months on another protocol and is available for transfer, biopsy will not be repeated unless clinically indicated. Fiducials will not be implanted again if previously placed and visible.
6. Six months following treatment, patients in both arms will undergo repeat 18F-DCFPyL imaging only if pretreatment imaging was informative.
7. If an 18F-DCFPyL study was performed within 4 months prior to enrollment on a different protocol, it will not be repeated at baseline. In patients treated with androgen deprivation therapy that was initiated within 4 months of a DCFPyL obtained on another protocol, this DCFPyL scan may be used as the baseline scan if the patient remains on ADT and the scan was obtained within 12 months of enrollment.
8. +/- 2 weeks at and after 6 month time point.
9. May be completed by remote visit with a member of the study team (e.g., if the patient is not able to return to the NIH CC). Remote visits will be conducted in compliance with NIH, FDA regulations and local policy. A patient may be referred to their local provider or asked to come to the NIH CC for an in-person assessment, if clinically indicated, and at the discretion of the PI. In the case of any visits with participants' local providers, records will be obtained.
10. Vital signs may be omitted during follow up visits if a patient is unable to return at the NIH clinical center and if the clinical evaluation does not indicate a need for collection.
11. As PSA is a standardized test and the results are comparable across laboratories, if the patient is not able to return to the NIH Clinical center, PSA may be obtained locally. If biochemical failure (PSA elevation at least 2 ng/dL above post-radiotherapy nadir) is identified, the second measurement will be obtained for confirmation per **6.3.2**, ideally at the NIH Clinical Center.

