4 CONCOMITANT MEDICATIONS/MEASURES

Supportive care with blood components, antibiotics, analgesics, and general medical therapy will be provided if the need relates to the performance of protocol assessments (biopsy and imaging procedures) or to treat side effects of therapy. Every effort will be made to refer the patient to their collaborating physician in the community for care unrelated to the protocol therapy or procedures. There are no limitations on the type of non-investigational concurrent medications allowed, as in general, these patients do not receive additional therapy for prostate cancer after radiotherapy, with the exception of hormonal therapy, which will not be delivered on this trial. Concurrent use of androgen deprivation therapy will be allowed but discouraged.

Radiation related side effects will be managed as per the current standard of care without restrictions in medications or procedures that may be performed for management.

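### ADT-exposed men have no scheduled route into bPFS: no testosterone is planned after baseline, 10.3 contradicts 6.3.3, and their nadir can be a PSA taken before testosterone recovery

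*Combined protocol and SAP*

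**What the plan says.** Section 6.3.3 restricts who counts for bPFS: "Patients who have been treated with androgen deprivation therapy within 3 months before or during this study will not be evaluable for the bPFS endpoint", and this lasts "until their testosterone is within the institutional limit of normal for at least two sequential measurements spaced by 1 month". In the same section bPFS runs from the start of treatment. Failure is a PSA more than 2 above the post-treatment nadir, confirmed by a second value at least 1 month later.

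Section 6.3.2 defines that nadir: "The post-SBRT nadir is the lowest PSA measurement obtained after treatment on this protocol". It makes no exception for PSA values taken on ADT or while testosterone is low.

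Testosterone appears in one row of the calendar (3.6), "CBC, Acute care panel, LFTs, Testosterone, PT/PTT, Viral serologies 2 | X", and the only mark is in the screening/baseline column. Section 2.2 asks for "PSA, testosterone, Alk Phos, ALT, AST, Bilirubin), PT, PTT within 4 weeks of study entry" and section 2.4 for "PSA, Testosterone, PT, PTT, Hepatitis B, and Hepatitis C (within 4 weeks of study entry". Section 3.5 adds PSA and correlative studies for two years, not testosterone. Section 6.1.1 names testosterone values and ADT use among the data to be captured, without a visit or timing.

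Section 10.3 sets a different population: one completed post-treatment PSA makes a man evaluable for biochemical control and biochemical relapse-free survival. It has no ADT or testosterone condition.

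The plan expects such men. Section 4 states: "Concurrent use of androgen deprivation therapy will be allowed but discouraged". Calendar footnote 7 covers men with an earlier scan from another protocol: "this DCFPyL scan may be used as the baseline scan if the patient remains on ADT".

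**The concern.** The gate in 6.3.3 depends on a measurement that the visit schedule does not produce, and the statistical section describes a population without the gate. Two analysts could follow the protocol in good faith and reach different answers on whether an ADT-exposed man is in the analysis.

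If he is in, a second problem follows. PSA is low while testosterone is suppressed and can rise when it recovers. The nadir rule lets the suppressed value serve as the reference. The two-value confirmation protects against a transient bounce, but not against a sustained rise to a new level.

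bPFS at 1 and 2 years is the trial's measure of tumour control, and 10.1 sets it against a 75% rate from brachytherapy series. Dropping these men loses information. Keeping them on a suppressed nadir can add false failures.

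**Working it through.** The plan gives no calculation for this rule, so there is no figure to reproduce. The check is a count, a comparison of sections, and simple arithmetic.

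**1. Draws needed and draws scheduled.** Needed (6.3.3): 2 sequential normal values. Scheduled after baseline (3.6): 0. The draws in 2.2 and 2.4 both fall within 4 weeks (28 days) of study entry, so they do not reliably give two values a month apart. They also say nothing about a man on ADT during follow-up.

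**2. Spacing.** Follow-up PSA visits are at 1, 3, 6, 9, 12, 15, 18, 21 and 24 months: 9 visits with gaps of 2 months, then 3 months. Even with testosterone added to every visit, no two consecutive visits are 1 month apart. Read literally, the spacing still fails. With at least 1 month, the first possible post-treatment pair is months 1 and 3.

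**3. Sections side by side.**
- 6.3.3 with 3.6: the man stays out of bPFS unless somebody orders testosterone outside the schedule.
- 10.3: the same man is in after his first post-treatment PSA.
- 6.3.2 applies in either case once he is in, with no adjustment to the nadir.

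**4. Effect of the nadir.** Failure requires PSA > nadir + 2, in the protocol's units. For assumed suppressed nadirs of 0.05, 0.1, 0.2 and 0.5, the thresholds are 2.05, 2.1, 2.2 and 2.5. A man whose PSA settles at 2.3 after recovery is 2.3 − 0.1 = 2.2 above a nadir of 0.1, and a second value at 2.3 confirms failure. With a nadir of 0.5 the difference is 1.8 and he is not a failure. If the nadir were taken after recovery at 2.3, failure would require more than 2.3 + 2 = 4.3.

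**5. Possible size, by assumption only.** The documents do not give the ADT-exposed share f, nor the share m of controlled ADT-exposed men who would be misread. Take the 10.2 maximum of 42 evaluable men and a true bPFS of 75% in everyone. If exposed men are left out, n = 42 × (1 − f), rounded, and the table gives the exact binomial 95% interval width at about 75%. If they are kept and misread, observed bPFS = 0.75 × (1 − f × m).

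| f (assumed) | n if left out | 95% CI width | bPFS if kept, m = 50% | bPFS if kept, m = 100% |
|---|---|---|---|---|
| 0% | 42 | 0.27 | 75% | 75% |
| 10% | 38 | 0.30 | 71.25% | 67.5% |
| 20% | 34 | 0.30 | 67.5% | 60% |
| 30% | 29 | 0.33 | 63.75% | 52.5% |
| 50% | 21 | 0.39 | 56.25% | 37.5% |

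The exclusion and misreading columns are alternatives, not effects to be added. The intervals treat bPFS as a simple proportion with complete follow-up.

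**The case against.** Several counter-arguments have force.

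*Testosterone is anticipated.* Section 6.1.1 lists it for capture, and anyone applying 6.3.3 would have to order it. A reader might infer that testosterone is never obtained and that these men can never become evaluable. The documents do not support that; they show a missing schedule. But with ad hoc testing, entry depends on who happens to be tested and when, which is a selection problem.

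*The nadir may be meant to start at recovery.* Because 6.3.3 withholds evaluability until testosterone is normal, one can read PSA assessment, nadir included, as starting then. That reading is reasonable, but 6.3.2 does not say so, and under 10.3 there is no waiting period. Nor is the nadir suppressed in every exposed man: one whose testosterone had recovered before his first post-SBRT PSA is unaffected.

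*The group may be small.* Section 4 says hormonal therapy is not delivered on the trial and discourages concurrent use, and 10.2 calls its sample size likely over-estimated. This stands. No count of affected men can be drawn from the documents, and the low end of the table is as admissible as the rest.

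*The 3-month window.* A reader might infer that men whose ADT ended earlier have unrecognised low testosterone and falsely prolonged control. Baseline testosterone is measured, so it would not be unrecognised, and no figure in the documents shows that the window fails.

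*bPFS is secondary.* It is described by Kaplan-Meier and a Cox model, with no powered test. The MTD does not depend on it. This limits the weight of the point.

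**Conclusion.** The point holds as a fault in the definition and ascertainment of a secondary endpoint that should be corrected. Three facts come straight from the text: two normal testosterone values are required and none is scheduled after baseline; 6.3.3 and 10.3 disagree on who is evaluable; and the 6.3.2 nadir does not exclude PSA values taken on ADT or before testosterone recovery. The first two are certain. The third leads to false failure only in men with a post-SBRT PSA taken before recovery, and only if their recovered level exceeds the suppressed nadir by more than 2.

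The size is unknown because the ADT-exposed share is not given. The effect is nil if no man is exposed. At an assumed 20% it would be a loss of 8 of 42 men (42 − 34) if they are excluded, or an observed 67.5% against a true 75% if they are kept and half of the controlled ones are misread. The need for the change does not rest on those figures.

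**What to change.** Four linked changes:

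1. In 3.6, add testosterone to the existing follow-up PSA draws for ADT-exposed men. In 6.3.3, require the two normal values to be at least 1 month apart, so that scheduled visits can satisfy the rule. That section already uses this form for PSA confirmation.
2. In 6.3.2, for these men, take the nadir only from PSA values on or after the date testosterone recovery is confirmed.
3. In 6.3.3, have them join the bPFS risk set at that date (delayed entry). Because bPFS runs from the start of treatment, moving the nadir alone would credit them with event-free time in which PSA failure could not be recorded.
4. Reconcile 10.3 with 6.3.3 on who is evaluable, and report bPFS with and without ADT-exposed men, stating how many there are and how many never enter.

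The cost is a few extra assays and short edits to 3.6, 6.3 and 10.3. Because footnotes 9 and 11 allow remote visits and local PSA, the calendar should also say whether a local testosterone value counts. The downside is later entry and shorter follow-up for these men. No treatment changes.
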